### Missing data

Missing outcome data (accelerometer data) will exclude the child from the study population. Missing data on predictors (CPUP and questionnaire data, including personal factors) will be handled by multiple imputation by multivariate imputation using chained equation (MICE) including all predictors and 100 imputation samples.

In model 2a and 2b the imputation will be performed before applying the lasso, and afterwards the predictors will be ordered by proportion of imputation sets in which they are included. From this prioritized list, we will construct a final prediction model including all predictors included in at least 50% of the

imputation sets, but other cutoffs than 50% will be evaluated by an elbow plot, and if a different cutoff appears convincing from the plot, this cutoff will be applied.

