## 6. Variable description

### Outcome

Daily average accelerometer counts will be used as outcome variable. The child/adolescent is encouraged to wear the belt with the Axivity AX3 accelerometer for seven consecutive days, but must have worn the accelerometer for a minimum of four days, including one weekend day, to be included in this study. The variable, daily average accelerometer counts, is weighted 5/7 and 2/7 for weekdays and weekend days, respectively.

Accelerometry data is collected 6-15 months post index date (see study diagram below).

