#### **Regression models**

Models will be checked using graphic inspection of diagnostic plots. Splines will be used to account for non-linear effects, and interactions will be included in the model based on relevant subject-matter knowledge. The coefficient of determination, adjusted R-squared, will illustrate the percentage of variance in PA that is explained by the predictive variables. The higher the coefficient, the stronger the relationship. The root mean squared error of the estimate will indicate the accuracy of the predictions.

The following models will be applied:

- Model 1
  - a) Multiple linear regression analysis between accelerometer counts (response variable) and all CPUP variables within each ICF component (predictive variables), using the latest CPUP registration prior to accelerometer data collection.
  - b) Multiple linear regression analysis between accelerometer counts (response variable) and all questionnaire variables within each ICF component (predictive variables), using the questionnaire data.
- Model 2
  - a) Penalized regression (lasso) with accelerometer counts as the response variable and covariates as chosen by lasso to obtain an optimal fit from model 1a as predictive variables to determine which variables to retain in the model.
  - b) Penalized regression (lasso) with accelerometer counts as the response variable and covariates as chosen by lasso to obtain an optimal fit from model 1b as predictive variables to determine which variables to retain in the model.

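### The imputation model does not name the accelerometer outcome; followed literally, it usually biases Model 1 slopes of incomplete predictors toward zero

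*Combined protocol and SAP*

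**What the plan says.** The Missing data part of section 7 is the only description of the imputation model in this document. What is to be imputed is described as "Missing data on predictors (CPUP and questionnaire data, including personal factors", and these gaps "will be handled by multiple imputation by multivariate imputation using chained equation (MICE) including all predictors and 100 imputation samples". In that section the outcome appears only as a reason for leaving a child out: "Missing outcome data (accelerometer data) will exclude the child from the study population".

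Elsewhere the SAP keeps outcome and predictors apart. Section 6 states: "Daily average accelerometer counts will be used as outcome variable". The Regression models part describes Model 1a as a regression between "accelerometer counts (response variable) and all CPUP variables within each ICF component (predictive variables", and Model 1b is the same with questionnaire variables. Tables 2 and 3 report a coefficient, 95% confidence interval and p-value for each variable and an adjusted R-squared for each ICF component. The SAP says the "adjusted R-squared, will illustrate the percentage of variance in PA that is explained by the predictive variables".

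For Model 2: "In model 2a and 2b the imputation will be performed before applying the lasso". Predictors are then ranked by how often they are selected, and "we will construct a final prediction model including all predictors included in at least 50% of the" imputation sets, unless an elbow plot points to another cutoff.

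**The concern.** In the SAP's own vocabulary the response is not a predictor, so the sentence read as written produces an imputation model without accelerometer counts. Values imputed that way carry no association with the outcome beyond what the other predictors supply. Mixing them with observed values dilutes the slope of the incomplete variable.

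The study's objective is to identify predictors of habitual physical activity. If missingness is material, the coefficients and adjusted R-squared in Tables 2 and 3 would partly reflect which variables happen to be incomplete. The SAP expects gaps: it plans 100 imputations, and Table 1 has a row for missing cerebral palsy subtype, which is a Table 2 predictor. Age is calculated, and gender, region and GMFCS level have a parent-report source for children without CPUP data, so these may have few gaps.

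**Working it through.** The plan gives no figure on this point, so there is none to reproduce.

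**Inputs from the documents.** n = 78 for the CPUP models and 123 for the questionnaire models (Study size). Sixteen predictors in components of 4, 4, 2, 3 and 3 (Table 2). The outcome is complete in the analysed set, because a missing outcome excludes the child.

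**Assumptions.** Missing rates of 10, 20, 30 and 40%, missing completely at random; 8 of 16 predictors incomplete; normal predictors with pairwise correlation 0.3; residual SD 1. Four slopes are 0.3 (two on incomplete predictors, two on complete ones) and the rest 0.

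**Theory.** Take one incomplete predictor X, missing fraction m, with all other predictors Z in both the imputation and the analysis. The partial slope is the covariance of Y with the part of X not explained by Z, divided by the variance of that part. Observed values contribute (1 - m) of the covariance; imputed values contribute none; the variance is unchanged. So slope ≈ (1 - m)β: 0.90β at m = 0.10, 0.80β at 0.20, 0.60β at 0.40. Simulation with uncorrelated predictors gave 0.88-0.90, 0.77 and 0.50-0.54, close to this and somewhat lower in small samples.

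**Model 1 simulation.** 400 replicates, 20 imputations, four-variable component. Entries are the incomplete true predictor's slope as a share of its complete-data slope (standard error about 0.01-0.02).

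| Missing | n=78 omitted | n=78 included | Difference | n=123 omitted | n=123 included | Difference |
|---|---|---|---|---|---|---|
| 10% | 0.90 | 0.96 | 0.06 | 0.92 | 0.98 | 0.06 |
| 20% | 0.78 | 0.90 | 0.12 | 0.80 | 0.93 | 0.13 |
| 30% | 0.68 | 0.85 | 0.17 | 0.71 | 0.91 | 0.20 |
| 40% | 0.57 | 0.80 | 0.23 | 0.62 | 0.88 | 0.26 |

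The difference is the part due to omitting the outcome; what is still lost with the outcome included is a small-sample effect. A separate run of the same design gave 0.91 v 0.97, 0.78 v 0.90 and 0.69 v 0.84 at n=78 for 10, 20 and 30%, and 0.91 v 0.99 at n=123 for 10%: differences of 0.06, 0.12, 0.15 and 0.08. A smaller third run (120 replicates) gave 0.10 and 0.12 at 20% and 0.21 and 0.18 at 30% (n=78 and n=123), broadly in line. Component adjusted R-squared was 0.01-0.05 below its complete-data value with the outcome omitted and within 0.004 of it with the outcome included.

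**Direction.** With the outcome omitted, complete correlated predictors were inflated by 2-7%. In a four-predictor example (n=123, correlation 0.5) with a weak (0.1) and a strong (1.0) predictor both incomplete, the strong slope fell to 0.90, 0.80 and 0.67 at 10, 20 and 30% missing, while the weak one rose to about 0.11-0.125.

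**When the loss is smaller.** With six of eight predictors incomplete, correlation 0.4 and equal effects, a small run at n=78 and 30% missing completely at random gave shares of 0.88, 0.88, 0.89 and 0.94 omitted against 0.96, 0.95, 0.98 and 0.99 included, a difference of 5-9 points. Here predictors outside the component carry much of the missing information.

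**Model 2.** Same design, n=78, fixed 50% cutoff; complete data / outcome omitted / outcome included:

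| Missing | True incomplete retained | Null incomplete retained | Final adjusted R-squared |
|---|---|---|---|
| 10% | 0.93 / 0.90 / 0.92 | 0.34 / 0.33 / 0.41 | 0.43 / 0.41 / 0.44 |
| 20% | 0.93 / 0.87 / 0.92 | 0.34 / 0.30 / 0.53 | 0.42 / 0.38 / 0.45 |
| 30% | 0.92 / 0.80 / 0.94 | 0.36 / 0.31 / 0.79 | 0.44 / 0.38 / 0.51 |
| 40% | 0.94 / 0.70 / 0.99 | 0.38 / 0.26 / 0.98 | 0.43 / 0.36 / 0.64 |

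At n=123, null retention was 0.36 / 0.35 / 0.50 at 20% and 0.36 / 0.32 / 0.67 at 30%; adjusted R-squared was 0.42 / 0.38 / 0.44 and 0.42 / 0.37 / 0.45. The Model 2 results come from one simulation and were not repeated.

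**The case against.** The SAP is silent on the outcome; it does not exclude it. Its reference to all predictors may mean predictors from every ICF component, and the analysts may intend to include the outcome. The SAP also leans on a published protocol article that was not available here. This stands: a reader might infer that the plan commits to a faulty imputation, and the documents do not support that. They support only that the sentence, followed literally, leads there.

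The size rests on an assumed missingness rate, and at 10% the effect is small. This also stands. A reader might infer that each incomplete slope loses a share equal to its missing fraction. That holds only when all predictors are fitted together, whereas Model 1 is fitted component by component and the all-variable regression has been eliminated. Nor should the whole shortfall be charged to the omission: at n=78 and 20% missing, 12 of the 22 points are attributable to it.

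A reader might also infer that every coefficient shrinks. The weak-and-strong example shows otherwise.

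The most serious objection is that including the outcome is no plain gain for Model 2. At n=78 and 20% missing, true retention rises by 0.05 (0.87 to 0.92) while null retention rises by 0.23 (0.30 to 0.53). This stands, so the remedy must differ between the models. Restricting each imputation equation to the outcome and same-component predictors may look like a way out. It contradicts the stated use of all predictors, and in Table 3 it would impute residence region and PedsQL, each alone in its component, from accelerometer counts only.

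**Conclusion.** The point holds for Model 1, on two conditions: the sentence is followed literally, and predictor missingness is material. Incomplete predictors' slopes are then usually pulled toward zero and correlated complete predictors slightly inflated. The loss due to omitting the outcome is about 6-8 percentage points of the slope at 10% missing, 12-13 at 20% and 15-20 at 30%, and less where other components inform the imputation strongly.

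These figures assume normal predictors, values missing completely at random and one correlation pattern. Categorical predictors were not simulated, and the n=123 runs used Table 2's grouping rather than Table 3's. For Model 2 the documents and simulations do not support a blanket claim that adding the outcome improves selection; there it is a trade-off that the SAP should make visible. The point should be fixed; confidence in its size is medium.

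**What to change.** For Models 1a and 1b, reword the imputation sentence along these lines: *MICE will include all predictors and covariates together with the outcome (daily average accelerometer counts), with 100 imputations.* Add that the missing fraction of each predictor will be reported.

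For Model 2, state whether the outcome is in the imputation model, and report the lasso selections with and without it as a sensitivity check. Note that including it can raise selection of null incomplete predictors and make adjusted R-squared optimistic when missingness is about 20% or more, most of all at n=78. If the outcome is left out on purpose because the aim is prediction, say so and give the reason.

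The cost is a few SAP sentences, one more variable in the imputation command and a second imputation run for Model 2. No new data are needed.

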#### Study size

The expected study size of 300-400 children, as mentioned in the protocol article, was obtained for consent given to participate. However, due to the COVID-19 pandemic, and consequences thereof, accelerometer data was only obtained for 123 children. Furthermore, due to the incompleteness of registered children in the CPUP database, only 78 of these children are eligible for analysis with CPUP data.

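### The imputation is specified without the outcome or any spline or interaction term, so such effects shrink toward zero where the predictor is incomplete

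*Combined protocol and SAP*

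**What the plan says.** Under Regression models (section 7), the commitment is unconditional: "Splines will be used to account for non-linear effects, and interactions will be included in the model based on relevant subject-matter knowledge". No variable, knot or interaction is named.

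Under Missing data (section 7), "Missing data on predictors (CPUP and questionnaire data, including personal factors) will be handled by multiple imputation", by chained equations "including all predictors and 100 imputation samples". For the lasso models, "In model 2a and 2b the imputation will be performed before applying the lasso". A child without outcome data leaves the analysis: "Missing outcome data (accelerometer data) will exclude the child from the study population". The outcome is therefore complete in every analysed child and available to the imputation, but the text does not say that it enters.

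Nothing else describes the imputation. Statistical software adds only the package and that seeds will be set. Exposure and adjustment variables (section 6) uses the word predictors for the questionnaire and CPUP variables themselves, not for terms derived from them.

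**The concern.** An imputation model should be at least as rich as the analysis model that follows. If missing values of a predictor are drawn from equations that hold only straight-line main effects, the imputed children carry no curvature and no interaction. Mixed with the observed children, they dilute these effects in the fitted model. If the outcome is also left out, the imputed values are unrelated to it given the other predictors, and the linear effects shrink as well.

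Models 1a and 1b are the primary analysis. Tables 2 and 3 report coefficients, and adjusted R-squared for each ICF component. Several listed predictors are scores or quantities that could carry a spline and could be incomplete: GMFM-66, range of motion, sleep hours, screen time, PODCI and PedsQL. Models 2a and 2b impute before the lasso, so any derived terms offered to the lasso would inherit the loss.

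**Working it through.** The SAP states no figure that depends on the imputation model, so there is nothing to reproduce. The consequence was checked by simulation.

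**Inputs from the SAP (Study size).** "accelerometer data was only obtained for 123 children" and "only 78 of these children are eligible for analysis with CPUP data", so n = 123 and n = 78.

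**Assumptions, not in the SAP.** One incomplete continuous predictor x and one complete predictor w, correlation 0.4. The outcome is y = 0.4x + 0.3w + 0.3x² + 0.3xw + N(0, 1). The quadratic stands in for a spline. Values of x are missing completely at random in 10%, 20% or 30%. Imputation is by normal regression with parameter draws, using 10 imputations per replicate; the mean estimate does not depend on using 100. There were 1,000 replicates (400 for the compatible method).

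**Measure.** Share retained = mean estimate / true value. For example, at n = 78, 20% missing, outcome included linearly, x² gives 0.239 / 0.30 = 0.80.

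Mean estimates (true value 0.40 for x, 0.30 for x² and for xw):

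| n | Missing | Predictors only: x | x² | xw | Outcome added linearly: x | x² | xw | Compatible: x² | xw |
|---|---|---|---|---|---|---|---|---|---|
| 78 | 10% | 0.357 | 0.264 | 0.283 | 0.395 | 0.263 | 0.281 | 0.305 | 0.296 |
| 78 | 20% | 0.319 | 0.229 | 0.272 | 0.382 | 0.239 | 0.265 | 0.305 | 0.292 |
| 78 | 30% | 0.284 | 0.193 | 0.245 | 0.384 | 0.199 | 0.253 | 0.303 | 0.300 |
| 123 | 10% | 0.358 | 0.269 | 0.281 | 0.394 | 0.268 | 0.286 | 0.305 | 0.291 |
| 123 | 20% | 0.315 | 0.234 | 0.264 | 0.397 | 0.235 | 0.268 | 0.300 | 0.307 |
| 123 | 30% | 0.276 | 0.196 | 0.249 | 0.382 | 0.207 | 0.243 | 0.299 | 0.300 |

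With no data missing, the estimates were 0.294 to 0.302 for x² and 0.298 to 0.304 for xw.

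**Reading the table.**
- Predictors only: the curvature loses about 10-12%, 22-24% and 35-36%, and the interaction about 6%, 9-12% and 17-18%. The linear effect falls from 0.40 to about 0.36, 0.32 and 0.28.
- Outcome added linearly: the linear effect returns to 0.38-0.40, but curvature and interaction stay attenuated.
- Imputation compatible with the analysis model: both return to 0.291-0.307.

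**Second setting.** Correlation 0.5, true curvature -0.3, residual SD 0.9, missing completely at random, outcome included linearly. Curvature kept about 0.90, 0.80 and 0.70 of its value at 10%, 20% and 30% missing. Adjusted R-squared fell from about 0.39-0.40 with full data to about 0.38, 0.35 and 0.34. At 5% missing, curvature kept about 94%; a true interaction of 0.5 with a binary variable kept 96-98%. At n = 78 and 20% missing, curvature was detected in 72% of runs after linear imputation, 87% with complete cases and 93% with full data.

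**The case against.** **The SAP is silent; it does not exclude.** It says including, not only, and an analyst could count derived terms among the predictors. This stands: the fault is an incomplete specification. But section 6 uses the word for variables, and a literal reading gives the mismatched imputation.

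**Exposure may be limited.** Many listed predictors are categorical or ordinal. GMFCS level is an inclusion criterion and age is calculated at the index date, so both are likely to be complete. Table 1 has a missing-data row only for CP subtype. This stands too: only incomplete predictors that carry a spline or interaction are affected.

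**Sampling error is large at these sizes.** In the second setting at n = 78, the root mean squared error of the curvature estimate was 0.087 with linear imputation and 0.087 with the squared term imputed jointly at 10% missing, and 0.095 against 0.092 at 20%. Interval coverage was 96% and 95%. At 30% missing it fell to 92% (n = 78) and 90% (n = 123). So up to about 20% missing the harm is mainly systematic shrinkage and lost power, not failed intervals.

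**Two stronger readings are tempting.** A reader might infer that the study would wrongly declare non-linearity or interaction absent. The documents do not support that: the objective is to identify predictors, and no planned table tests linearity or has an interaction row. A reader might also infer that a complete-case analysis would be better. Its estimates were close to the truth here only because data were assumed missing completely at random. When missingness depended on the outcome, complete-case curvature fell to 81-89% of the truth.

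**The remedy has limits.** Imputing the squared term as a further variable can be noisier: with missingness dependent on the outcome, at n = 78 and 10% missing, its root mean squared error was 0.108 against 0.094 for linear imputation. Substantive-model-compatible imputation restored curvature and adjusted R-squared with equal or lower error in the second setting with data missing completely at random, which is why it is preferred.

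**Conclusion.** The point holds as an under-specification with a predictable bias if the text is followed literally. Spline and interaction effects that involve an incomplete predictor shrink toward zero and adjusted R-squared is understated. If the outcome is also omitted, linear effects shrink too.

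The size rests on assumed data missing completely at random, a quadratic in place of a spline, and one incomplete predictor. Under those assumptions the curvature loss is roughly equal to the fraction missing: about 10%, 20% and 30% at 10%, 20% and 30%, somewhat more at 30% in the first setting. Interactions lose less, and at 5% missing or below the loss is small. Because the SAP reports no missingness rates, the bias in this study may be negligible or material. It should be settled in the SAP because all analyses are to follow its publication.

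**What to change.** Add to the Missing data section wording to this effect:

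> The imputation for each model includes the accelerometer outcome and is compatible with the spline and interaction terms in that model, preferably by substantive-model-compatible chained equations, or else with the derived terms imputed as further variables. A small set of such terms is listed in advance, and the imputation is re-run if a term is added after the diagnostic plots.

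Reporting the proportion missing for each predictor would let readers judge how much this mattered.

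The cost is SAP wording, a little more code and possible re-runs; no new data are needed. The real constraint is sample size. Table 2 already lists 16 predictors, several with more than two categories, for 78 children in Model 1a, so the number of spline and interaction terms must stay small for the imputation to be estimable.

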### Statistical software

All statistical analyses will be performed using Stata/IC 17 or later for Windows (Stata-Corp LLC, College Station, TX, USA). Random seeds will be specified for imputation.

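### Models 2a/2b: selecting predictors by a vote over 100 imputation sets leaves borderline variables dependent on the random seed; 1,000 sets would reduce this cheaply

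*Combined protocol and SAP*

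**What the plan says.** The Missing data section (SAP section 7) specifies chained-equation imputation of predictors, "including all predictors and 100 imputation samples". For Models 2a and 2b, imputation comes before the lasso, and "the predictors will be ordered by proportion of imputation sets in which they are included". The default rule for the final model is "including all predictors included in at least 50% of the" imputation sets. The same sentence makes the cutoff provisional, and a replacement takes effect if the plot supports it: "other cutoffs than 50% will be evaluated by an elbow plot, and if a different cutoff appears convincing from the plot, this cutoff will be" [...].

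The Regression models section describes the lasso step as using "covariates as chosen by lasso to obtain an optimal fit from model 1a as predictive variables". It does not say whether the penalty is chosen by cross-validation, an information criterion or another rule. On reproducibility, the Statistical software section says "Random seeds will be specified for imputation" and mentions no seed for the lasso.

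The Study size section states that "accelerometer data was only obtained for 123 children", of whom 78 can be analysed with CPUP data. Tables 4 and 5 will show the selected variables. The Protocol deviations section classes Model 2 as the secondary analysis.

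**The concern.** One hundred imputations are ample for pooling regression coefficients. Here they have a second job: the count of sets in which the lasso picks a predictor decides whether it appears in the final model at all. That count is a simulation estimate, and a yes/no decision near a threshold is far more sensitive to simulation error than a pooled average is.

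At stake is the list of variables in Tables 4 and 5. Two analysts following the plan on the same children, with different seeds, could report lists that differ in a borderline variable. That difference would carry no information about the children.

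**Working it through.** The documents give no figure for the stability of the selection, so there is nothing of the plan's own to reproduce.

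**Inputs from the SAP.** M = 100 sets and default cutoff 50% (Missing data); n = 78 for CPUP data and n = 123 with accelerometry (Study size); 16 candidate rows in each of Tables 2 and 3, more once categories and splines are expanded. The SAP does not give the fraction of missing predictor data, the strength of the effects or the penalty rule. These are assumed in step 3.

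**Step 1: Monte Carlo error.** For given data, the number of sets selecting a predictor is approximately binomial (M, p), where p is its long-run share. The standard error of the observed share is sqrt(p(1-p)/M).

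- M = 100, p = 0.5: sqrt(0.25/100) = 0.050, or 5.0 points (95% range about ±9.8).
- M = 1,000, p = 0.5: sqrt(0.25/1000) = 0.0158, or 1.6 points (about ±3.1).
- At another cutoff the error is similar. At 30% or 70% with M = 100 it is sqrt(0.21/100) = 0.046.

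**Step 2: retention at a 50% cutoff.** With t = P(X ≥ M/2), two independent seeds disagree with probability 2t(1-t).

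| True share | Retained, M = 100 | Seeds disagree, M = 100 | Retained, M = 1,000 | Seeds disagree, M = 1,000 |
|---|---|---|---|---|
| 35% | 0.1% | 0.3% | 0.0% | 0.0% |
| 40% | 2.7% | 5.3% | 0.0% | 0.0% |
| 45% | 18.3% | 29.9% | 0.1% | 0.2% |
| 48% | 38.2% | 47.2% | 10.9% | 19.4% |
| 50% | 54.0% | 49.7% | 51.3% | 50.0% |
| 52% | 69.2% | 42.6% | 90.3% | 17.6% |
| 55% | 86.5% | 23.3% | 99.9% | 0.1% |
| 60% | 98.3% | 3.3% | 100.0% | 0.0% |
| 65% | 99.9% | 0.2% | 100.0% | 0.0% |

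The seed-sensitive band is roughly 40-60% with 100 sets. With 1,000 sets it shrinks to a few points either side of 50%. A predictor at exactly 50% stays a coin toss at any M.

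**Step 3: how often the whole list changes.** This depends on how many predictors fall in the band, so it needs assumptions. All runs below used a fixed 50% cutoff. Each percentage is the share of simulated data sets, or paired runs, in which the final list differed between two seeds.

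| Assumptions | n = 78 | n = 123 |
|---|---|---|
| 18 columns, R² 0.30, cross-validation, 2 / 5 / 10% missing, 40 data sets per cell, M = 100 | 12 / 22 / 45% | 22 / 22 / 35% |
| Same, BIC penalty (no folds), M = 100 | 8 / 18 / 25% | 12 / 8 / 15% |
| 18 columns, R² 0.30, 10-fold cross-validation, 10% missing, M = 100 | 49% | 29% (48 data sets) |
| Same, M = 1,000 | 17% (5 of 30; exact 95% CI 6-35%) | not run |
| 16 predictors, R² 0.35, 10% missing, imputation seed changed with folds fixed, 36 data sets, M = 100 | 44% | 44% |

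A further BIC run (5-10% missing, 24 data sets per cell) gave about 20-27% with 100 sets and 7-13% with 1,000. In the first two rows the mean number of variables changing was 0.08-0.75 of 18. When a list did change, it was usually by about one variable.

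**Step 4: folds, only if cross-validation is used.** With the imputed data held fixed, redrawing the folds in every set changed the list in 31-33% of cases at n = 78 and 17% at n = 123. If one fold split was reused for all sets and that split was then changed, the list changed in 56% and 50%. More imputation sets cannot average out a single shared split, so the fold scheme matters as well as its seed.

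**The case against.** Four points can fairly be made for the plan.

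- **The cutoff is not fixed.** A reader who stops at the 50% rule might infer a hard threshold. The documents do not support that, because the elbow plot may replace it, and an elbow placed at a gap in the shares could avoid the knife edge modelled above. This stands as a limit on the figures. It does not remove the issue: the plot is drawn from the same noisy shares, and whatever cutoff results is still a yes/no rule.
- **Most predictors are stable.** Outside roughly 40-60% at a 50% cutoff, 100 sets give nearly the same answer under any seed. This stands. Nor does Monte Carlo error depend on the number of children; a small sample matters only in that it can leave more predictors near the cutoff.
- **An imputation seed is already promised.** That makes one run repeatable, which counts in the plan's favour. It does not show that another seed would give the same list.
- **Cross-validation is never stated.** A reader might infer that the missing fold seed is a defect. It is one only if folds are used; with an information criterion there is nothing to seed. The vote noise remains without folds, as the BIC results show.

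It would also be too strong to quote 49% as the expected rate of disagreement. It sits at the top of a range driven by inputs that the SAP does not give.

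**Conclusion.** The point holds as a minor one. The Monte Carlo error in steps 1 and 2 follows from the SAP's own M = 100 and default 50% cutoff: up to 5 points, enough to make predictors within about 10 points of the cutoff depend on the seed. How often this changes a published list is uncertain. Roughly 8-49% of simulated data sets is the range over 2-10% missingness, BIC or cross-validated tuning, and n = 78 or 123, all with a fixed 50% cutoff and few data sets per cell.

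The documents do not support the inference that the selection as a whole is arbitrary, or that more computing would remove the problem. The change usually concerns about one borderline variable in a secondary analysis, and a predictor very close to the cutoff stays unstable at any number of sets. Model 1 does not use this vote and is unaffected.

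**What to change.** Amend the Missing data, Regression models and Statistical software sections as follows:

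1. Use 1,000 imputation sets for the selection step of Models 2a and 2b. Model 1 can stay at 100. The standard error at 50% falls from 5.0 to 1.6 points.
2. Report each candidate's inclusion proportion with Tables 4 and 5. Mark as borderline any predictor within about 3 points of the cutoff used (2 × 1.6 = 3.2). This covers the predictors that extra sets cannot settle.
3. State how the lasso penalty is chosen. If by cross-validation, give the number of folds, say whether they are redrawn in each imputation set, and set a seed for them as well as for the imputation.

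The cost is SAP wording and computing time. No new data are needed.
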